#### **Drug** accountability

To have complete control over the distribution and use of the study medication, the drug accountability must be performed before new medication is handed out to the subject.

#### 8.8 Post-study therapy

Further treatment at the end of the study will be at the discretion of the investigator.

At the conclusion of the study, patients who demonstrate clinical benefit may be eligible to continue to receive study drug. They may receive further treatment, assessments and/or be followed either via a roll-over study - subject to approval by the competent health authority and ethics committee - or through any other mechanism in accordance with local legal and compliance rules. This applies to patients on study treatment and in follow-up.

In the event a roll-over study is established, the present study will end when all patients have transitioned into the roll-over study or discontinued from this study for another reason (e.g. consent withdrawn, lost to follow-up, death). Until the transition to the roll-

 Modified by Amendment 7, see Section 15.6.2.17

17 Oct 2018 Version 8.0 Page: 67 of 395

over study, patients will continue to follow all the procedures and visits required in the current version of the protocol.

## 8.9 Prior and concomitant therapy

For prior therapy, see Section 7.1.2 (Exclusion criteria "Medication, drug use and special behavioral patterns").

Medication other than the investigational product must not be taken during the study without consulting the investigator.

All therapies that are considered necessary for the subject's welfare and that are not expected to interfere with the evaluation of the study drug may be given at the discretion of the investigator.

Disease-specific anti-neoplastic therapies, including kinase inhibitors, chemotherapy, radiation therapy, or surgical intervention, are not allowed during study treatment.

All concomitant medications (including start / stop dates, total daily dose, and indication) must be recorded in the subject's source documentation and in the eCRF. Concomitant use of contrast media needs not to be recorded unless the subjects experiences and AE and there is a reasonable possibility that the event might have been caused by exposure to contrast media.

## 8.9.1 Drug-drug interactions relevant for BAY 1163877

Oxidative metabolism of BAY 1163877 is mainly catalyzed by CYP3A4 and CYP1A1 and to a lesser extent by CYP2C9. Therefore, drugs and herbal preparations that are strong inhibitors and inducers of CYP3A4 are not permitted during the study. Currently, there are no known approved drugs or herbal preparations that are strong CYP1A1 inhibitors or inducers. However, it should be noted that CYP1A1 is induced in smokers. The subjects who are current smokers and those with recent history of smoking may have lower plasma concentrations of BAY 1163877.

Initial *in vitro* study results with BAY 1163877 indicate minor mechanism-based (irreversible) inhibition potential towards CYP 3A4. Since several commonly used drugs are metabolized by CYP 3A4, subjects should be proactively closely monitored for side effects of these comedications due to potentially increased systemic exposure.

In general, subjects should be closely monitored for side effects of all concomitant medications regardless of elimination pathway, especially those with narrow therapeutic index. If possible, narrow therapeutic index drugs that are CYP3A4 substrates should be avoided (see Section 16.11).

No data are available to evaluate the interaction between BAY 1163877 and radiation.

#### **8.9.2** Prohibited concomitant therapy

Concomitant therapy with the following medication is NOT allowed:

• Anticancer chemotherapy or immunotherapy during the study or within 5-half-lives prior to start of study treatment. Antibody treatment should not be given within 6

17 Oct 2018 Version 8.0 Page: 68 of 395

weeks before starting to receive study treatment. Acute toxic effects of previous anticancer chemotherapy or immunotherapy have to be normalized completely (excluding alopecia, anemia and / or hypothyroidism). Anticancer therapy is defined as any agent or combination of agents with clinically proven anti-tumor activity administered by any route with the purpose of affecting the malignancy, either directly or indirectly, including palliative and therapeutic endpoints.

- Mitomycin C, nitrosoureas or monoclonal antibodies with anticancer activity (e.g. bevacizumab or cetuximab etc.) should not be given within 6 weeks before starting to receive study treatment or within 6 weeks of pre-treatment biopsy for biomarker (p-ERK1/2) studies in case of performed biopsy procedure
- Bone marrow transplant or stem cell rescue.
- Investigational anti-tumor agents or anti-neoplastic chemo / hormonal / immunotherapy.
- Radiotherapy to target lesions (palliative radiotherapy is allowed)
- CYP3A4 inhibitors and inducers: BAY 1163877 is mainly metabolized by CYP3A4 and CYP1A1 and to a lesser extent by CYP2C9. Therefore, concomitant use of strong inhibitors of CYP3A4 and strong inducers of CYP3A4 are not permitted for 2 weeks prior to start of study treatment or during the study. Concomitant use of moderate and weak CYP3A4 inducers should be avoided as clinically significant decrease in plasma concentrations of BAY 1163877 cannot be ruled out. Strong CYP3A4 inhibitors and inducers are shown in Section 16.11.
- Concomitant use of herbal preparations containing CYP3A4 inducers (e.g. St John's Wort) are not permitted during the study.
- Grapefruit and grapefruit juice (CYP3A4 inhibitor) consumption is not permitted during the study.
- If possible, narrow therapeutic index drugs that are CYP3A4 substrates (e.g. alfentanil, cyclosporine, dihydroergotamine, ergotamine, fentanyl, pimozide, quinidine, sirolimus, and tacrolimus) should be avoided
- Fluconazole is considered a moderate to strong inhibitor of CYP 2C9 and should be avoided, if possible.
- Therapies that are known to increase serum calcium and / or phosphate levels, especially calcium, phosphate, vitamin D, parathyroid hormone (parathormone).

Therapeutic monitoring should be performed consistent with the local clinical standard of care following dose modification of the investigational agent. In general, subjects should be closely monitored for side effects of all concomitant medications regardless of path of elimination.

## 8.9.3 Permitted concomitant therapy - amended

• Subjects may receive supportive care for any underlying illness, including dexamethasone, G-CSF and other hematopoietic growth factors to treat acute toxicities,

No. BAY 1163877 / 16443

17 Oct 2018 Version 8.0 Page: 69 of 395

such as febrile neutropenia, when clinically indicated or at the investigator's discretion.

- Additional concomitant medications such as low dose heparin, gonadotropin releasing hormone agonist or antagonist, antihistamines and intravenous fluid supply are permitted, if clinically indicated
- In view of the maximum dose of 800 mg b.i.d., a risk for clinically relevant drug interaction due to inhibition of BCRP and/or P-gp in the intestine for drugs with a low bioavailability limited by P-gp and BCRP cannot be ruled out. However, based on the maximum achievable plasma BAY 1163877 concentration, risk of clinically relevant drug interaction due to systemic inhibition of BCRP and P-gp is regarded as low.
- Subjects taking narrow therapeutic index medications should be monitored proactively.
- Antiemetic therapy is allowed.
- Treatment with "non-conventional therapies" (such as acupuncture), and vitamin / mineral supplements are permitted provided that they do not interfere with the study endpoints, in the opinion of the investigator (to be documented in the source notes and in the eCRF).

#### 9 Procedures and variables

## 9.1 Schedule of procedures

Time deviations from the given time points will be documented as protocol deviations, if applicable. Respective time windows for visits are specified in the flow chart (see Section 16.1).

#### 9.1.1 Tabulated overview

See study flow charts in Section 16.1.

#### 9.1.2 Timing of assessment

If not stated otherwise, the measures listed in the following sections will be performed by or under the supervision of an investigator.

The same imaging or measuring method must be used for all tests required at baseline (screening) and follow-up.

 Added by Amendment 7

No. BAY 1163877 / 16443

17 Oct 2018 Version 8.0 Page: 70 of 395

#### 9.1.2.1 Pre-treatment

# 9.1.2.1.1 FGFR expression / FGFR mutation testing (MTD expansion cohorts only) - amended

A separate subject information sheet / informed consent form (SIS / ICF) for FGFR expression / FGFR mutation testing must be signed by all subjects recruited for study Part 1, Part 2 or Part 3 MTD expansion cohort (see Section 13.2).

The following activities / examinations will be performed prior to FGFR expression / FGFR mutation testing:

- Signed informed consent for FGFR expression / FGFR mutation testing
- Inclusion criteria limited to FGFR expression / FGFR mutation testing (see Section 7.1.1.1)
- ECOG performance status assessment
- Demographic data
- Documentation of the primary diagnosis (refractory, locally advanced or metastatic solid tumor) using the complete pathological report
- Complete medical /oncological history, TNM classification (see Section 9.2.3)
- Obtain archival tumor tissue sample for FGFR expression / FGFR mutation testing
   Only, if no archival tumor tissue sample is available which has been handled and processed as described in the lab manual: Perform a biopsy to obtain fresh tumor material
- Toxicity / AE assessment and recording only in case an invasive procedure will be performed to obtain tumor material after subjects' informed consent

All subjects enrolled into the study will be listed on a subject enrollment log provided by the sponsor's representatives.

#### 9.1.2.1.2 Screening - amended

Pre-study examinations will be performed within 7 days / within 28 days before first administration of BAY 1163877 (i.e. before Cycle 1, Day 1). Due to the fact that not all subjects may fulfill the inclusion / exclusion criteria, a higher number of subjects, than needed to be valid for the evaluation of the study, will be asked to participate in the pre-study (screening) examination. As soon as fulfillment of all criteria is confirmed, the subject is included into the trial. In case all subjects are equally qualified, decision will be made by the sponsor or sponsor representative casting lots.

-

 Part 3 added by Amendment 7, see section 15.6.2.19

17 Oct 2018 Version 8.0 Page: 71 of 395

[figure not shown]
Study specific required screening examinations will only be performed after having received the subject's written IC for study treatment eligibility. The subject information sheet / informed consent form (SIS / ICF) for study treatment eligibility must be signed by all subjects including those subjects presenting FGFR expression / FGFR mutation who have signed the SIS / ICF for FGFR expression / FGFR mutation testing before (see Section 9.1.2.1.1)

The following examinations will be performed prior to the first study drug administration:

## Within 28 Days Prior to First Dose of BAY 1163877

- Signed informed consent for study treatment eligibility (within 28 days or earlier), see Section 13.2.
- Inclusion / exclusion criteria
- Demographic data (already collected for subjects of Part 1, Part 2 or Part 3 MTD expansion cohorts, see Section 9.1.2.1.1) 55
- Documentation of the primary diagnosis (refractory, locally advanced or metastatic solid tumor) using the complete pathological report (already done for subjects of Part 1, Part 2 MTD expansion cohorts or Part 3, see Section 9.1.2.1.1)
- Complete medical / oncological history, TNM classification (see Section 9.2.3) (already done for subjects of Part 1, Part 2 or Part 3 MTD expansion cohorts, see Section 9.1.2.1.1)
- Concomitant diseases and NYHA grading
- Review of baseline toxicities
- Baseline characteristics (smoking habits / history, alcohol consumption )
- Previous and concomitant treatment (medication history up to 4 months prior to start of study treatment, see Section 7.1.2)
- Physical examination with complete review of body systems (see Section 9.5.3.1)
- ECOG performance status assessment (also for subjects of Part 1, Part 2 or Part 3 MTD expansion cohorts, see Section 9.1.2.1.1)
- Single 12-lead ECG reading (see Section 9.5.3.4)
- Send subject to consultant ophthalmologist for ophthalmological examination (see Section 9.5.3.2). New onset of cataract or other abnormalities affecting lens or cornea lead to the exclusion of the subject.
- CT scans of the chest, abdomen and pelvis; CT scans of other metastatic lesions as applicable or MRI and documentation of lesion(s) according to RECIST, v1.1. CT/MRI

<sup>55 Part 3 added here and in the following by Amendment 7, see section 15.6.2.20

17 Oct 2018 Version 8.0 Page: 72 of 395

scans prior screening can be used for documentation according to RECIST, v1.1, if scans were done the latest 28 days prior to first dose of BAY 1163877 (see Section 9.3.1)

- Virology tests, for details see Table 16-4
- Obtain pre-treatment biopsy:
  - optional for subjects in the dose escalation cohorts of study Part 1 (all comer)
  - mandatory for all subjects in the MTD expansion cohort of Part 1 (all comer).
  - optional for subjects in the MTD expansion cohort of Part 2 (sqNSCLC + LAC + BC + SCCHN)
  - mandatory for all subjects in the study Part 3 / MTD expansion "Safety cohort" (sqNSCLC + LAC + BC)
  - Note 1: A biopsy is mandatory for all subjects in the MTD expansion cohort of Part 1, Part 2 and Part 3 for whom no archival biopsy is available for FGFR expression / FGFR mutation testing. Additional biopsy is not requested if a biopsy was already obtained for FGFR expression / FGFR mutation testing prior to the screening visit (see Section 9.1.2.1.1).
  - Note 2: Anticancer chemotherapy must have been stopped for at least 5 half-lives of the last applied therapy before the pre-treatment biopsy for biomarker (p-ERK1/2) studies is taken. Mitomycin C, nitrosoureas or monoclonal antibodies with anticancer activity (e.g. bevacizumab or cetuximab etc.) should not be given within 6 weeks of pre-treatment biopsy for biomarker (p-ERK1/2) studies.

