Electrocardiogram (ECG): 12-lead ECG readings will be performed at screening, on Cycle 1, Days -3 and -2 ("tablet bridging cohort" and "food effect assessment", only), on Cycle 1, Days 1, 2, and 15, thereafter on Day 1 of each subsequent Cycle, and at the EOT visit. In all Cycles and at the EOT visit, ECG readings will be performed as single readings. The time points for ECG readings and further details are provided in Section 9.5.3.4.

Pharmacodynamic (PD) biomarkers: In an attempt to demonstrate the mechanism of action of BAY 1163877 biomarkers will be studied in tissue samples (for details see Section 9.4.4).

Biomarker analysis in tumor tissue: Biomarker analysis will be done at screening for subject stratification in the MTD expansion cohorts (Part 1: all comer; Part 2: sqNSCLC + LAC + BC + SCCHN; Part 3: sqNSCLC + LAC + BC) according to FGFR expression levels / FGFR mutation using either an archival tumor tissue specimen or fresh tumor biopsy material (see Section 7.1.1, inclusion criteria).

Analysis of phospho-extracellular signal-regulated kinase 1/2 levels, (p-ERK1/2) will be done at screening and on Cycle 2, Day 1 for all subjects of study Part 1 and Part 2 who are willing to undergo a biopsy both at screening and on Cycle 2, Day 1. Both biopsies are mandatory for "all comer" subjects included in the MTD expansion cohort of Part 1 (please refer to Section 7.1.1 for details).

Tumor response evaluation: Computed tomography (CT) or magnetic resonance imaging (MRI) of all anatomic regions involved with the disease will be performed at screening (baseline), at the end of Cycle 2 and thereafter every third cycle to assess tumor response using the Response Evaluation Criteria in Solid Tumors, Version 1.1. (RECIST v1.1)(1).

Response evaluation according to RECIST v1.1 can be done up to 5 days after CT / MR scan.

**Recommended Phase II dose (RP2D)**: The dose recommended for Phase II studies with BAY 1163877 will be determined by the investigators and the sponsor (DSMT) at the end of this study (after Part 2) after having reviewed the data from all dose levels evaluated including PK data, overall incidence and severity of AEs, cardiac safety, and amount of MTD.

<sup>36 Part 3 - Safety cohort - was added by Amendment 7, see section 15.6.2.6

<sup>37 Part 3 was added by Amendment 7, see section 15.6.2.6

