## Study Part 3 / "Safety cohort" (sqNSCLC + LAC + BC)

Preliminary safety data of patients with advanced cancer treated with BAY 1163877 showed a favorable safety profile (details can be found in the current version of the IB). However, sample size is still limited in selected indications (sqNSCLC, LAC, BC) and additional safety data will be generated in Study Part 3 "Safety cohort". In parallel, additional efficacy data will be collected and changes of selected immune parameters will be assessed in Part 3.

<sup>39 The following section was added by Amendment 7, see section 15.6.2.7

17 Oct 2018 Version 8.0 Page: 46 of 395

It was shown that FGFR3 expression is inversely correlated to programmed death-ligand 1 (PD-L1) expression and T cell infiltration in tumor tissue of patients with BC (40). This finding was confirmed in archival biopsy samples collected in study 16443. A similar correlation was detected in patients with sqNSCLC and LAC in study 16443.

Recently, the PD-1 and PD-L1 inactivating antibodies received accelerated approval by the FDA for patients with BC. It was demonstrated that patients with a low expression of PD-L1 had a smaller chance to respond to atezolizumab treatment.

It is assumed that a causal relationship between FGFR expression and T cell exclusion leads to low PD-L1 levels and decreased responsiveness towards inhibition of the PD-L1 axis. Potentially, inhibition of FGFR can overcome this interaction and render tumors targetable by the immune system.

Immune responses and the tumor microenvironment are inadequately reflected in preclinical cancer models. We therefore aim to analyze selected immune parameters before and during BAY1163877 treatment in paired biopsies and in serum of biomarker-selected cancer patients. Fresh tumor tissue will be used to assess immune parameters indicating a T cell response against the tumor tissue. This will be done by performing gene expression profiling (nCounter PanCancer Immune Profiling Panel) and immunohistochemistry for CD8+ T cell infiltration and PD-L1 expression on the tumor tissue. Peripheral blood will be used to collect serum to determine cytokine levels (IL-6, IFN-gamma, and other cytokines if needed). Aim of the assessment of peripheral blood is to search for changes in this easily accessible specimen that reflect the immune response in the tumor tissue.

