#### 7.1.2.1 Exclusion criteria for FGFR expression / FGFR mutation testing (only for MTD expansion cohorts of study Part 1)

- No archival biopsy available and no consent to obtain tumor biopsy.
- Subject still on anticancer treatment or in the washout period of a previous anticancer treatment (defined as 5 half-lives of the anticancer agent [or 6 weeks for mitomycin C, nitrosureas and monoclonal antibodies]) at the time the fresh biopsy would be obtained if no archival biopsy is available

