#### 7.1.2.2 **Exclusion criteria for FGFR expression / FGFR mutation testing** (only for MTD expansion cohorts of study Part 2 and Part 3) amended44

No archival biopsy available and no consent to obtain tumor biopsy.

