#### Medication, drug use and special behavioral patterns

- Prior treatment with BAY 1163877. Subjects permanently withdrawn from study participation will not be allowed to re-enter the study.
- Concomitant therapies that cannot be discontinued or switched to a different medication prior to study entry that are known to increase serum phosphate levels are not permitted within 4 weeks prior to start of study treatment).
- Anticancer chemotherapy or immunotherapy during the study or within 5-half-lives prior to start of study treatment. Mitomycin C, nitrosoureas or monoclonal antibodies with anticancer activity (e.g. bevacizumab or cetuximab etc.) should not be given within 6 weeks before starting to receive study treatment or within 6 weeks of pre-treatment biopsy for biomarker (p-ERK1/2) studies. Acute toxic effects of previous anticancer chemotherapy or immunotherapy have to be normalized completely (excluding alopecia). Anticancer therapy is defined as any agent or combination of agents with clinically proven anti-tumor activity administered by any route with the purpose of affecting the

No. BAY 1163877 / 16443

17 Oct 2018 Version 8.0 Page: 52 of 395

malignancy, either directly or indirectly, including palliative and therapeutic endpoints.

- Use of strong inhibitors of CYP3A4 and strong inducers of CYP3A4 should have been stopped 2 weeks before start of study treatment (see Section 16.11).
- Radiotherapy to target lesions during study or within 3 weeks of start of study treatment. Palliative radiotherapy is allowed.
- Use of systemic corticosteroids within 2 weeks of start of study treatment above the Cushing threshold
- Autologous bone marrow transplant or stem cell rescue within 4 months of start of study treatment
- Major surgery, open biopsy or significant traumatic injury within 4 weeks of start of study treatment
- Subjects undergoing renal dialysis

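### In the text available, the washout tied to the pre-treatment biopsy covers p-ERK1/2 studies only, so the Part 3 immune tissue baseline is protected only by the washout counted back from first dose

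*Protocol*

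**What the plan says.** The Protocol ties a prior-therapy washout to the pre-treatment biopsy in several places: the Synopsis inclusion criteria, 7.1.1.2, 7.1.2.3 (medication), 8.9.2, 9.1.2.1.2 Note 2 and 9.4.4. Each time it is limited to one purpose. Chemotherapy must have been stopped for five half-lives "before the pre-treatment biopsy for biomarker (p-ERK1/2) studies is taken". Mitomycin C, nitrosoureas and anticancer antibodies "should not be given within 6 weeks of pre-treatment biopsy for biomarker (p-ERK1/2) studies".

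The p-ERK1/2 analysis is described in Section 6 as being done "for all subjects of study Part 1 and Part 2 who are willing to undergo a biopsy", and 9.4.4 lists p-ERK1/2 biopsies for Parts 1 and 2 only. The Part 3 biopsy serves another purpose. Section 6.2 says: "We therefore aim to analyze selected immune parameters before and during BAY1163877 treatment in paired biopsies and in serum of biomarker-selected cancer patients". Section 9.4.1.2 makes a fresh biopsy mandatory at screening and again in Cycle 2, for immune gene expression, CD8+ infiltration and PD-L1, and states no washout.

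Two further passages bear on the baseline:

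- **FGFR-testing stage.** For Part 1, 7.1.2.1 excludes a subject who is on anticancer treatment or in washout "at the time the fresh biopsy would be obtained if no archival biopsy is available". For Parts 2 and 3, 7.1.2.2 has a single criterion: "No archival biopsy available and no consent to obtain tumor biopsy".
- **Re-use.** Note 1 in 9.1.2.1.2, which names Part 3, says: "Additional biopsy is not requested if a biopsy was already obtained for FGFR expression / FGFR mutation testing prior to the screening visit". Section 9.1.2.1.1 gives the testing visit no time limit before first dose.

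A general washout does apply to every part. Sections 7.1.2.3 and 8.9.2 bar chemotherapy and immunotherapy during the study or within five half-lives of first dose. For mitomycin C, nitrosoureas and anticancer antibodies, 7.1.2.3 bars dosing "within 6 weeks before starting to receive study treatment or within 6 weeks of pre-treatment biopsy for biomarker (p-ERK1/2) studies".

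**The concern.** The Part 3 exploratory objective rests on a within-subject change from a baseline biopsy to a Cycle 2 biopsy, with no control group. Prior chemotherapy or an anti-PD-1/PD-L1 antibody can itself alter CD8+ infiltration and PD-L1 staining. If the baseline is taken soon after such therapy, the change mixes recovery from it with any effect of FGFR inhibition.

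The Protocol accepts this reasoning for p-ERK1/2 and protects that baseline. It does not extend the protection to the immune endpoints, although footnotes show that Amendment 7 both added the Part 3 biopsy and touched the washout notes. Section 6.2 mentions recent approval of PD-1 and PD-L1 antibodies in bladder cancer, so prior exposure is plausible.

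**Working it through.** The plan gives no sample size, power or error rate for this objective (10.7), so there is no stated figure to reproduce. The check is date arithmetic.

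**Inputs**

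- Antibody washout before first dose: 6 weeks = 42 days (7.1.2.3, 8.9.2).
- Chemotherapy and immunotherapy washout before first dose: 5 half-lives (same sections).
- Screening biopsy window: up to 28 days before first dose (9.1.2.1.2).
- Part 3 serum cytokine baseline: within 7 days before first dose (9.1.2.1.2).
- Half-lives: not given in the Protocol; the values below are assumptions.

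**Formula.** Let W be the washout required before first dose and b the days from biopsy to first dose. The shortest permitted gap from last prior therapy to biopsy is W - b. For a p-ERK1/2 biopsy the gap is W itself, so the shortfall is b.

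**Antibodies, six-week rule (W = 42)**

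- Biopsy on day -28: 42 - 28 = 14 days
- Day -21: 42 - 21 = 21 days
- Day -14: 42 - 14 = 28 days
- Day -7: 42 - 7 = 35 days
- A p-ERK1/2 biopsy on any of these days: 42 days

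**Antibodies, if the five-half-life immunotherapy rule also binds them.** That rule is stricter once 5 × half-life exceeds 42 days, that is, above 42 / 5 = 8.4 days. For a day -28 biopsy:

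- assumed half-life 14 days: 70 - 28 = 42 days
- assumed half-life 21 days: 105 - 28 = 77 days

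**Chemotherapy, five half-lives.** The required interval is shorter than 28 days when the half-life is below 28 / 5 = 5.6 days. Counting from first dose alone, a day -28 biopsy could then precede the last chemotherapy dose:

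- assumed half-life 1 day: last dose allowed up to day -5
- assumed half-life 3 days: up to day -15
- assumed half-life 7 days: 35 - 28 = 7 days, one half-life

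**Re-used FGFR-testing biopsy.** With no limit on b, W - b has no lower bound.

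**Serum cytokines.** With b at most 7, the gap after the last antibody is at least 42 - 7 = 35 days.

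**With the p-ERK1/2 condition applied to Part 3.** The minimum antibody gap for a day -28 biopsy rises from 14 to 42 days, and the chemotherapy gap becomes five half-lives whatever the biopsy day.

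**The case against.** The strongest reply is that Part 3 does have a washout, counted back from first dose, and that a reader might wrongly infer there is none. That stands. It also limits how far the antibody case goes. The 14-day gap holds only under the six-week rule; a checkpoint antibody is plausibly also immunotherapy, and with a long half-life the gap can equal or exceed 42 days. A baseline taken while a checkpoint antibody is still being given cannot arise from an in-window biopsy, only from a re-used earlier one.

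Second, the bar on anticancer therapy during the study may already rule out chemotherapy around the biopsy, because the Synopsis and Section 6 count pre-treatment as part of the on-study period. This is a fair reading but not a settled one: it would make the separate Part 1 criterion in 7.1.2.1 redundant.

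Third, Note 1 may mean only that no second biopsy is needed for FGFR testing, since 9.4.1.2 makes a fresh screening biopsy mandatory in Part 3. Section 9.1.2.1.1 also allows a fresh testing biopsy only when no suitable archival sample exists, so the route concerns a subset. As worded, though, Note 1 does not exclude re-use.

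Fourth, Table 16-8, the Part 3 biomarker schedule, was not in the text available and could carry a washout note. That remains open.

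Finally, the objective is exploratory and 10.1 rules out confirmatory analysis. This limits the stakes; it does not supply the missing condition.

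**Conclusion.** The concern holds for the tissue baseline. No biopsy-tied washout in the text available covers the Part 3 immune biopsy, the Part 1 testing-stage safeguard is absent for Part 3, and Note 1 leaves re-use of an earlier biopsy open. The shortfall against the p-ERK1/2 condition equals the days between biopsy and first dose: up to 28 days for a screening biopsy, unbounded for a re-used one.

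Three stronger conclusions are tempting but not supported:

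- That the change cannot be attributed to BAY 1163877 at all. Attribution is limited by the uncontrolled design in any case; the wording adds confounding in affected subjects only.
- That a particular share of the roughly 40 Part 3 baselines is affected. The documents give no figure, and the approvals mentioned in 6.2 do not show how many enrolled subjects had such therapy.
- That the serum cytokine baseline is equally exposed. It is largely protected by its 7-day window.

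The conclusion assumes that Table 16-8 contains no overriding note. The chemotherapy result further assumes that the bar during the study does not reach the screening period.

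**What to change.** Reconcile 7.1.2.1, 7.1.2.2, 7.1.2.3, 8.9.2, 9.1.2.1.2 (Notes 1 and 2), 9.4.1.2 and 9.4.4, with the matching Synopsis text, so that the biopsy-timing condition already used for p-ERK1/2 also covers the Part 3 immune biopsy. The mandatory screening biopsy would be scheduled after the existing washout and before first dose. Check Table 16-8 for consistency.

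State in Note 1 whether an earlier FGFR-testing biopsy may serve as the Part 3 immune baseline.

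Base the main paired tissue analysis on pairs whose baseline meets the condition and report the others separately. Rejecting a non-conforming biopsy outright could mean another invasive procedure, so an analysis flag is preferable. The information needed is largely collected already: medication history for four months before treatment (9.1.2.1.2) and prior anticancer therapy (9.2.3).

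The cost is a wording amendment, tighter timing of the screening biopsy for some subjects, and a few pairs outside the main exploratory analysis.
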